11.6.2.2. Visit 3 (Day 7 ± 2)

The following study-related procedures will be performed at Visit 3; it is suggested that they be performed in the order presented below, as is possible by the site:

- Administer MADRS.
- Administer HAM-A.
- Administer YMRS.
- Administer QIDS-SR16.
- Administer AIMS.
- Administer BARS.

- Administer Modified SAS.
- Administer C-SSRS (Since Last Visit version).
- Administer CGI-BP-S.
- Record prior and concomitant medications.
- Record adverse events.
- Obtain vital signs, including orthostatic changes in blood pressure and heart rate.
- Perform 12-lead ECG.
- Ask subject the date and time of their last 3 doses of study drug and record in the source.
- Collect used/unused study drug and packaging.
- Perform study drug accountability.
- Dispense study drug.
- Instruct subject to dose once daily in the morning approximately the same time each day at home.
- Schedule next visit:
 - Instruct subject to take the morning dose prior to the clinic visit. Clinic visits are to begin no later than 6 hours postdose, if possible.
 - Instruct subject to record date and time of the last 3 doses prior to next visit and to bring back all used/unused study drug and packaging to the next visit.

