6.5. WINDOWING CONVENTIONS

Apart from early termination data (see [Section 6.3](#)), no visit windowing will be performed during the analysis for this study. Data will be summarized by analysis visit and analyzed by week where applicable (see [Section 6.3](#)).

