6.8. SOFTWARE VERSION

Apart for the supplementary analysis of the primary endpoint exploring the dose response relationship (generalized MCP-Mod using the DoseFinding package, version 0.9-16) which will use R software version 3.5.3 or higher (R Foundation for Statistical Computing, Vienna, Austria), all other analyses will be conducted using Statistical Analysis System (SAS[®]) version 9.4 or higher (SAS Institute, Inc., Cary, North Carolina).

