16.1.1. PRIMARY EFFICACY VARIABLE & DERIVATION

The primary efficacy endpoint is the change from baseline in the MADRS total score at Week 6.

The MADRS is a clinician-rated assessment of the subject's level of depression. The measure contains 10 items that measure apparent and reported sadness, inner tension, reduced sleep and appetite, difficulty concentrating, lassitude, inability to feel, and pessimistic and suicidal thoughts. Each item is scored in a range of 0 to 6 points, with higher scores indicating increased depressive symptoms. Total

Document:

Author:

Version Number:

V2.0

Version Date:

21MAY2020

Template No: CS_TP_BS016 Revision 4
Effective Date: 01Apr2016

Reference: CS_WI_BS005

score will be equal to the sum of the 10 items (range between 0 and 60). MADRS is assessed at Visit 1/Screening, Visit 2/Baseline/Week 0, Visit 3/Week1, Visit 4/Week 2, Visit 5/Week 4, and Visit 6/Week 6.

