Between group effect size will be defined as: Natural Log(odds ratio)xsqrt(3)/pi

The NNT will be derived as 1/Risk Reduction where Risk Reduction (RR) = (SEP-4199 trt group – placebo response rate). The NNT results will be provided in whole numbers with any fractional values rounded up to the nearest whole number.

The 95% CI will also be presented (only when the lower and upper limits are of the same sign) and are computed by taking the reciprocal of the 95% lower and upper bound of the RR. The lower confidence limit will be rounded down to the largest integer value that is less than the computed estimate, and the upper confidence limit will be rounded up to the smallest integer value that is greater than the computed estimate.

Cochran-Armitage test for trend will be used to test for association between MADRS response and the three treatments.

The log rank testing method will be used to test for differences among the treatments for time to MADRS response. ITT subjects discontinuing the study and those completing the study without meeting the criteria for MADRS response will be censored at the date of last dose of study drug or, if unknown, the end of study date. The analysis will be supplemented with Kaplan-Meier curves to illustrate the differences among the three treatments. A Cox proportional hazards model will also be used with treatment, region, and baseline value as parameters. Wald Chi-square p-value will be included.

A cumulative distribution curve for all treatment groups will be presented, plotting the cumulative percent of MADRS responders versus the percent reduction at Week 6 from baseline.

16.3.3.6. MADRS remission at Week 6

Remission incidence rate, defined as MADRS total score ≤ 12 , will be analyzed similarly to the MADRS responder analysis, including the sensitivity analysis of observed values and of assessing the removal of remote visits (see [Section 16.3.3.5](#)).

Subjects with MADRS total scores ≤ 10 and ≤ 8 at Week 6 will be summarized using descriptive statistics.

A cumulative distribution curve for all treatment groups will be presented, plotting the cumulative percent of MADRS remissions versus the MADRS total score at Week 6.

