PROC LIFETEST OUTSURV=PROBRESPONSE TIMELIST=(9 16 30 44);  
  TIME RSPTIME*RSPSTAT(1);  
  STRATA TRTPN / DIFF=CONTROL ('Placebo');  
RUN;
```

```
ODS OUTPUT HAZARDRATIOS=HAZARDRATIOS PARAMETERESTIMATES=PARAMETERESTIMATES;PROC PHREG;  
  CLASS REGION TRTP (REF='Placebo') / PARAM=REF;  
  MODEL RSPTIME*RSPSTAT(1)=TRTP REGION TOTBL;  
  HAZARDRATIO TRTP / DIFF=REF;  
  CONTRAST '200 MG VS. PLACEBO' TRTP 1 0 / ESTIMATE;  
  CONTRAST '400 MG VS. PLACEBO' TRTP 0 1 / ESTIMATE;  
RUN;
```

Document:

Author:

Version Number:

V2.0

Version Date:

21MAY2020

Template No: CS_TP_BS016 Revision 4
Effective Date: 01Apr2016

Reference: CS_WI_BS005

LOGISTIC REGRESSION

* Placebo is reference;
PROC LOGISTIC DESCENDING;
 CLASS TRTPN REGION / PARAM=REF;
 MODEL RESP = TRTPN REGION TOTBL;
 CONTRAST '200 MG vs. PLACEBO' TRTPN 1 0 / ESTIMATE=EXP;
 CONTRAST '400 MG vs. PLACEBO' TRTPN 0 1 / ESTIMATE=EXP;
 CONTRAST '200 MG vs. 400 MG' TRTPN -1 1 / ESTIMATE=EXP;
CONTRAST '(200 MG + 400 MG) vs Placebo' TRTPN 0.5 0.5 / ESTIMATE=EXP;RUN;

COCHRAN-ARMITAGE TEST

```
PROC FREQ;  
    TABLE TRTP*RESP/CMH TREND;  
RUN;
```

MULTIPLICITY-ADJUSTED P-VALUES

*Example raw p-values;
DATA STUDY;
 INPUT HYP \$ FAMILY PARALLEL \$ SERIAL \$ RAWP;
 DATALINES;
 H1 1 0000 0000 0.1403
 H2 1 0000 0000 0.0095
 H3 2 0000 1000 0.0559
 H4 2 0000 0100 0.0051
 ;
RUN;

%TREEGATE(TEST=HOCHBERG, GAMMA=0.9);

Document:

Author:

Version Number:
Version Date:

V2.0
21MAY2020

Template No: CS_TP_BS016 Revision 4
Effective Date: 01Apr2016

Reference: CS_WI_BS005

PATTERN MIXTURE MODEL (PMM) WITH PLACEBO BASED MI

The steps to implement this sensitivity analysis are as follows. For Japan cohort analysis, code must be adapted by removing REGION variable.

Step 1: Intermittent missing MADRS total scores will be imputed for each treatment using non-missing data from all ITT subjects within the treatment group by a Markov Chain Monte Carlo (MCMC) imputation model which assumes a multivariate normal distribution over all variables included in the imputation model. This imputation is based on the MAR assumption, ie, the missing data are assumed to follow the same model as the other patients in their respective treatment group.

```
PROC MI DATA=xxx OUT=yyy NIMPUTE=1000 SEED=12345 MINIMUM=. . 0 0 0 0 MAXIMUM=. . 60 60 60 60  
MINMAXITER=100;  
    BY TRTP;  
    VAR REGION MADRS_BASE MADRS_Wk1 MADRS_Wk2 MADRS_Wk4 MADRS_Wk6;  
    MCMC CHAIN=MULTIPLE IMPUTE=MONOTONE NBITER=5000 NITER=200;  
RUN;
```

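### The supplementary Cox model for time to MADRS response names no tie method, so SAS's default Breslow approximation pulls the hazard ratio slightly toward 1 (log HR about 2-5% smaller if response time is the actual study day)

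*SAP*

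**What the plan says.** Time to response (at least a 50% fall in MADRS from baseline) is one of the other endpoints in Protocol 6.4 and SAP 2.6.4. The planned test is in SAP 16.3.3.5: "The log rank testing method will be used to test for differences among the treatments for time to MADRS response". Kaplan-Meier curves accompany it. The SAP then adds: "A Cox proportional hazards model will also be used with treatment, region, and baseline value as parameters", with a Wald chi-square p-value. Protocol 15.3.5.3 plans the log-rank test and the curves but no Cox model.

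The PHREG statement in SAP Appendix 3 is "MODEL RSPTIME*RSPSTAT(1)=TRTP REGION TOTBL". It has no `TIES=` option. The only such option in the SAP is in a PROC RANK step for safety parameters. On software, SAP 6.8 says that, apart from the dose-response modelling, "all other analyses will be conducted using Statistical Analysis System".

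On when response can be seen, SAP 16.1.1 says: "MADRS is assessed at Visit 1/Screening, Visit 2/Baseline/Week 0, Visit 3/Week1, Visit 4/Week 2, Visit 5/Week 4, and Visit 6/Week 6". Protocol 11.6.2.2 to 11.6.3 put the four post-baseline visits at Days 7, 14, 28 and 42, each ±2 days.

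`RSPTIME` is not defined. Two passages bear on it. SAP 6.5 says that, apart from early-termination data, "no visit windowing will be performed during the analysis for this study". The Kaplan-Meier code uses "PROC LIFETEST OUTSURV=PROBRESPONSE TIMELIST=(9 16 30 44", and these values are the upper ends of the four visit windows.

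**The concern.** When several subjects have an event on the same recorded day, the Cox partial likelihood has to be approximated or computed exactly. Breslow's approximation keeps every tied subject in the risk set for every tied event. The denominators are then too large and the log hazard ratio is pulled toward zero. The error grows with the share of the risk set that has an event on the same day. Here about 98 subjects per arm can first meet the response criterion at only four scheduled visits, so ties are certain.

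What is at stake is the hazard ratio for each dose, its confidence interval and its Wald p-value. These will be reported beside a log-rank p-value for the same comparison that does not depend on the tie option. The two could differ because of an unstated software default.

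**Working it through.** The documents give no hazard ratio, event count or power for time to response, so there is no plan figure to reproduce.

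**Inputs from the documents.** 98 randomised per arm (SAP 3.4: 93 evaluable plus about 5%; 93/0.95 = 97.9). Four post-baseline visits at Days 7, 14, 28 and 42. A ±2-day window gives 5 possible days per visit, so 4 × 5 = 20 possible scheduled response days if actual dates are used, and 4 if nominal visits are used.

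**Assumptions not in the documents.** Placebo response by Week 6 of 30-50%; true HR 1.3-2.0; 15% dropout; constant or rising hazard. That PROC PHREG uses Breslow when `TIES=` is absent is a property of the software, not a statement in the documents.

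**Step 1, mechanism.** For d tied events, let S_R be the risk-set sum of exp(xβ) and S_D the same sum over the tied events. Breslow's denominator is S_R^d. Efron's is the product over l = 0, …, d−1 of (S_R − (l/d)·S_D). With two arms and one tied time, Breslow's score equation gives exp(β) = p1/p0, the ratio of event probabilities, whereas the hazard ratio is ln(1−p1)/ln(1−p0).

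Take 40% placebo response over 42 days at constant hazard, true HR 1.5 (ln 1.5 = 0.4055), nominal days:
- 14-day gap: p0 = 1 − 0.6^(1/3) = 0.157; p1 = 1 − 0.6^(1/2) = 0.225; ratio 1.440; ln 1.440 / 0.4055 = 0.90.
- 7-day gap: p0 = 1 − 0.6^(1/6) = 0.0816; p1 = 1 − 0.6^(1/4) = 0.1199; ratio 1.469; ln 1.469 / 0.4055 = 0.95.

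With two gaps of each length, Breslow should recover between 90% and 95% of the log HR.

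**Step 2, simulation.** Two arms, 98 per arm, 120 runs in each of 54 scenarios, every data set fitted with both methods. Breslow was closer to 1 in all 54. Selected rows, including the extremes of each range:

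| Placebo response, true HR, hazard | Response time | Efron HR | Breslow HR | Breslow/Efron log HR |
|---|---|---|---|---|
| 40%, 1.5, constant | nominal | 1.527 | 1.477 | 0.922 |
| 40%, 1.5, constant | actual, uniform over ±2 | 1.550 | 1.534 | 0.977 |
| 30%, 1.3, constant | nominal | 1.293 | 1.276 | 0.948 (highest nominal) |
| 50%, 2.0, rising | nominal | 1.996 | 1.815 | 0.862 (lowest nominal) |
| 30%, 1.3, constant | actual, peaked at nominal | 1.250 | 1.246 | 0.985 (highest actual) |
| 50%, 2.0, rising | actual, peaked at nominal | 1.900 | 1.840 | 0.950 (lowest actual) |

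The first row's 0.922 lies inside the 0.90-0.95 of Step 1. On nominal days the loss is 1 − 0.948 = 5% to 1 − 0.862 = 14%. On actual days it is 1 − 0.985 = 1.5% to 1 − 0.950 = 5%.

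A separate three-arm simulation (98 per arm, same assumed ranges, 18 settings) gave about 5-12% on nominal days and 1.5-3.5% on actual days, with Breslow below Efron in every setting.

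**Step 3, inference.** Standard errors agree to within 0.001, so the Wald z shrinks by the same factor. For 40% placebo response and HR 1.5 (SE 0.223), the shift is (ln 1.550 − ln 1.534)/0.223 = 0.05 SE on actual days and (ln 1.527 − ln 1.477)/0.223 = 0.15 SE on nominal days.

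**Step 4, comparison with the log-rank test.** Further runs used 300 data sets per setting, 40% placebo response and constant hazard. On nominal days with HR 1.5, mean z was 1.59 (Breslow), 1.72 (Efron) and 1.74 (log-rank), and rejection rates were 36%, 41% and 42%. With HR 2.0, mean z was 2.95, 3.23 and 3.30. On actual days with HR 1.5, the log HR was 0.398 against 0.408, a loss of 1 − 0.398/0.408 = 2.5%.

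**The case against.** The strongest reply is that this hardly matters. The SAP's wording points to actual days: no windowing outside early termination, censoring by date, and Kaplan-Meier time points at the ends of the visit windows. The loss is then a few percent of the log HR, well under one standard error. The Cox model is an addition to the log-rank test, is absent from the protocol, and concerns an endpoint outside the two hypothesis families in SAP 7.4. The bias is toward no effect, so it cannot create a false claim of benefit. The sizes also rest on response rates and hazard ratios that the documents do not give.

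All of this stands, and it sets the size and the priority. It does not remove the point. The default moves the estimate in a known direction, and the plan does not settle which size applies. SAP 6.4 maps early-termination efficacy data to planned visits, SAP 6.5 allows analysis by week, and time points of 9, 16, 30 and 44 would also work with nominal times.

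It is also fair to say that Efron repairs only the handling of ties. Response seen at visits is interval-censored, and the tie option does not change that.

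**Conclusion.** The point holds as a minor, free improvement. As written, the Cox analysis of time to MADRS response will use Breslow ties. Its log hazard ratio and Wald z will be about 2-5% too small if `RSPTIME` is the actual study day, the more likely reading, or about 5-14% too small if it is the nominal visit. Both ranges depend on the assumed placebo response of 30-50%, true HR of 1.3-2.0 and 15% dropout. The direction did not vary across scenarios.

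A reader might infer that a loss above 10% is the expected size. The documents do not support that: it needs response times collapsed to four nominal days and, within that coding, the higher assumed response rates or hazard ratios. A reader might also infer that the trial's conclusion on time to response is compromised. It is not. The planned test is log-rank, and neither it nor the Kaplan-Meier curves nor any primary or secondary analysis uses the tie option.

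**What to change.** 1. Append `/ TIES=EFRON` (or `/ TIES=EXACT`) to the PHREG MODEL statement in SAP Appendix 3, and name the method in SAP 16.3.3.5.
2. Define `RSPTIME` as the actual study day of the first MADRS assessment that meets the response criterion. If nominal visits are intended instead, say so; a discrete-time model such as complementary log-log would then suit the data better.
3. Use the same option in any Cox model fitted for time to remission. The SAP gives no remission-specific Cox code, so this applies only if one is run.

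The cost is one code option and one or two sentences. It needs no new data and leaves the multiplicity scheme untouched.

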18. PHARMACOKINETIC ANALYSIS

All PK analysis will be performed using PK population.

Blood sample for plasma concentrations of R-amisulpride, S-amisulpride, total amisulpride, and/or plasma prolactin measurement will be collected at Visit 1/Screening (only for plasma prolactin), Visit 2/Baseline/Day -1, Visit 4/Week 2, Visit 6/Week 6, and Visit 7/Follow-up/Week 7. The PK collection times from Predose on Day -1 to Follow-up and deviations and/or any values excluded from analysis will be presented in data listings. Any plasma concentration or summary statistics below the lower limit of Document:

Author:

Version Number:
Version Date:

V2.0

21MAY2020

Template No: CS_TP_BS016 Revision 4
Effective Date: 01Apr2016

Reference: CS_WI_BS005

quantification (LLOQ) will be represented by "BLQ" (below the limit of quantification) in tables and listings. Amisulpride plasma concentration will not be presented for the placebo group.

R-amisulpride, S-amisulpride, total amisulpride, and plasma prolactin concentrations at each scheduled sample collection time point (including ET and Follow-up, see [Section 6.3](#) for mapping of the ET visit) will be summarized descriptively (n, mean, median, minimum, maximum, coefficient of variation [CV] and if appropriate, geometric mean and geometric CV [GCV]). In addition, if there is at least 1 concentration < LLOQ within a treatment group at a time point, it will be set to $\frac{1}{2}$ LLOQ for summary statistics calculations. A second approach will be to assume a truncated normal distribution for the specific concentration data if at least 10% of the concentrations at a time point are < LLOQ within a treatment group. The mean and variance of truncated normal will be calculated ([APPENDIX 3](#)). Number and percentage of concentrations that are below the LLOQ will be provided for each visit. All PK summaries will be presented by dose.

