18.1. DERIVATION

LLOQ is 0.0500 ng/mL for R-amisulpride and S-amisulpride and LLOQ is 1.56 ng/mL for plasma prolactin.

Below derivations apply after concentrations lower than LLOQ are set to $\frac{1}{2}$ LLOQ.

- Coefficient of variation
$$100 * \text{Standard Deviation} / \text{Mean}$$
- Geometric Mean
$$\text{Exponential}(\text{mean of } \log_e \text{ transformed data})$$
- Geometric CV
$$\text{Square Root}(\text{Exponential}(\text{Variance}(\log_e \text{ transformed data}) - 1)) * 100$$

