 - o P-values should be reported to three decimal places, except values <1.000 but >0.999 will be presented as '>0.999' (eg, 0.9998 is presented as >0.999); and values <0.001 will be presented as '<0.001' (eg, 0.0009 is presented as <0.001). Rounding will be applied after the <0.001 and >0.999 rule.
- Ratios:
 - o Ratios should be reported to one more decimal place than the raw data.
- Spacing:
 - o There must be a minimum of 1 blank space between columns (preferably 2).
- Missing values:
 - o A "0" should be used to indicate a zero frequency.
 - o A blank will be used to indicate missing data in an end-of-text table or subject listing.
- Figures:
 - o Figures should be provided in RTF files using the SAS Output Delivery System (ODS), as Computer Graphics Metafile (CGM) formatted graphical output generated by SAS.
 - o The CGM file itself should contain the title or footer.
 - o The image should be clear and of high quality when viewed in the Word document, and when printed.
 - o In general, boxes around the figures should be used.
- Footers should be defined as follows:
 - o A continuous line of underscores ('_') will follow the body of the table or listing prior to any footnotes at the bottom of the page.
 - o Table footnotes should be defined using compute statements in the proc report, and should appear directly after the body of the table.
 - o If text wraps across more than one line (for a note), the first letter for all lines of text after the first one will be indented to align beneath the first letter of the text in the first line.

DATES & TIMES

Depending on data available, dates and times will take the form DDMMYYYYYYThh:mm:ss.

Document:

Author:

Version Number:
Version Date:

V2.0

21MAY2020

Template No: CS_TP_BS016 Revision 4
Effective Date: 01Apr2016

Reference: CS_WI_BS005

SPELLING FORMAT

English US.

PRESENTATION OF TREATMENT GROUPS

For outputs, treatment groups will be represented as follows and in that order:

Treatment Group	For Tables, Graphs and Listings
Placebo	Placebo
SEP-4199 200 mg	SEP-4199 200 mg
SEP-4199 400 mg	SEP-4199 400 mg
All SEP-4199	All SEP-4199 (only applies to tables)

LISTINGS

All listings will be sorted by the following (unless otherwise indicated in the template):

- Randomized/Actual treatment received as applicable, displaying SEP-4199 first and then placebo.
- Subject ID,

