    VAR REGION MADRS_BASE MADRS_WK1 MADRS_WK2 MADRS_WK4 MADRS_WK6;
    CLASS TRTP REGION;
    MONOTONE REGRESSION(/ DETAILS);
    MNAR MODEL(MADRS_WK1 MADRS_WK2 MADRS_WK4 MADRS_WK6/ MODELOBS = (TRTP = 'Placebo'));
RUN;

```

The MODEL option specifies that only observations where TRT = "Placebo" are used to derive the imputation model for the missing postbaseline MADRS scores. Thus, the TRT variable is not specified in the VAR list. This approach is also known as jump to reference (jump to placebo in our case) where it is assumed that the discontinuations from the SEP-4199 treatment groups immediately change to have the distribution of the placebo group. This imputation model is also the imputation model that is used to impute missing postbaseline observations in the placebo group.

Step 3: Fit the primary MMRM model using each of the 1000 imputed datasets (BY _IMPUTATION_) and calculate the inferential statistics on each imputed dataset.

```

PROC MIXED DATA=zzz;
    BY _IMPUTATION_;
    CLASS SUBJID REGION TRTP WEEK;
    MODEL TOTCFB = MADRS_BASE REGION TRTP WEEK TRTP*WEEK / DDFM=KR;
    REPEATED WEEK/TYPE=UN SUBJECT=SUBJID;
    LSMEANS TRTP*WEEK /PDIFF CL;
    ODS OUTPUT DIFFS=CHGDIFF LSMEANS=CHGLSMN;
RUN;

```

Step 4. Use proc MIANALYZE to combine the estimates from Step 3 based on Rubin's imputation rules. See example for LS Means below.

```

PROC MIANALYZE DATA = CHGLSMN;
    BY TRTP WEEK;
    MODELEFFECTS ESTIMATE;

```

Document:

Author:

Version Number:

V2.0

Version Date:

21MAY2020

Template No: CS_TP_BS016 Revision 4
 Effective Date: 01Apr2016

Reference: CS_WI_BS005

```
STDERR STDERR;  
ODS OUTPUT PARAMETERESTIMATES = LSMN (DROP = PARM);  
RUN;
```

TIPPING POINT ANALYSIS

This analysis assumes that the data in the SEP-4199 treatment groups is not missing at random. The tipping point based assumption will be used, ie, the trajectories of the subjects in the SEP-4199 treatment groups after withdrawal are assumed to be worse by an amount of delta, after the MI using the MAR assumption.

The steps to implement this sensitivity analysis are as follows. For Japan cohort analysis, code must be adapted by removing REGION variable.

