Step 1: Run the primary MMRM analysis for the ITT population. Obtain LS mean difference between each SEP-4199 group and the placebo group at each visit. Suppose these values are stored in variable LSMDIFF in dataset DIFF (LSMDIFF_200_PLACEBO, LSMDIFF_400_PLACEBO). This dataset should also contain the variable WEEK. These differences will be used when applying penalty on the imputed values.

Step 2: Similar to above, intermittent missing data will be filled in, assuming MAR, to obtain only monotone missing data.

```
PROC MI DATA=xxx OUT=yyy NIMPUTE=1000 SEED=12345 MINIMUM=. . 0 0 0 0 MAXIMUM=. . 60 60 60 60  
MINMAXITER=100;  
BY TRTP;  
VAR REGION MADRS_BASE MADRS_Wk1 MADRS_Wk2 MADRS_Wk4 MADRS_Wk6;  
MCMC CHAIN=MULTIPLE IMPUTE=MONOTONE NBITER=5000 NITER=200;  
RUN;
```

Step 3: Impute the remaining missing data using an MAR-based regression model.

```
PROC MI DATA = yyy OUT = zzz NIMPUTE = 1 SEED = 56789 MINIMUM= . . 0 0 0 0 MAXIMUM= . . 60 60 60 60  
MINMAXITER=100;  
BY _IMPUTATION_;  
VAR TRTP REGION MADRS_BASE MADRS_WK1 MADRS_WK2 MADRS_WK4 MADRS_WK6;  
CLASS TRTP REGION;  
MONOTONE REGRESSION;  
RUN;
```

Step 4: For a range of penalty values (ie, 5%, 10%, etc of the LS mean difference obtained in Step 1), apply penalty to the change from baseline values calculated from imputed MADRS total scores in each SEP-4199 group at each postbaseline visit.

Suppose ANALYSIS is the dataset reformatted from zzz that contains each subject's data in long format. It should contain the missing value flag MISSVAL (ie, whether the MADRS total score for a given visit is missing in the original data): 1 = missing; 0 = available. Other variables in analysis should

Document:

Author:

Version Number:

V2.0

Version Date:

21MAY2020

Template No: CS_TP_BS016 Revision 4
Effective Date: 01Apr2016

Reference: CS_WI_BS005

include: SUBJID, TRTP, REGION, WEEK, TOTBL, AVAL (MADRS total score at each postbaseline visit), TOTCFB, LSMDIFF, and _IMPUTATION_.

```
DATA ANALYSIS_PENALTY;
  SET ANALYSIS;
  /* store the original TOTCFB values in ORIGCHG */
  ORIGCHG = TOTCFB;
  /* if a MADRS total score is missing in the original dataset, apply a penalty to the TOTCFB value in each SEP-4199 group only */
  DELTA = XXX;
  IF MISSVAL=1 AND TRTP="200 MG" THEN TOTCFB = ORIGCHG - ((DELTA/100)* LSMDIFF_200_PLACEBO);
  IF MISSVAL=1 AND TRTP="400 MG" THEN TOTCFB = ORIGCHG - ((DELTA/100)* LSMDIFF_400_PLACEBO);
RUN;
```

Repeat the above step for all delta values, ie, 5, 10, ..., 100%.

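### The SAP's geometric CV formula misplaces the minus 1, its 200-versus-400 mg contrast prints the inverse odds ratio, and its trend test leaves the dose order unset

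*SAP*

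**What the plan says.** **Geometric CV.** SAP Section 18 has R-, S- and total amisulpride and plasma prolactin summarised at each time point, with "if appropriate, geometric mean and geometric CV [GCV". Section 18.1 defines the geometric CV, shown here with its typesetting codes, as "Square Root}(\text{Exponential}(\text{Variance}(\log_e \text{ transformed data}) - 1)) * 100". The bracket opened by the exponential closes after the minus 1.

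**Logistic contrasts.** In Appendix 3, Logistic Regression, a comment names placebo as the reference and the class variables use reference coding. The first contrast, 200 mg against placebo, has coefficients `1 0`. The second is "CONTRAST '400 MG vs. PLACEBO' TRTPN 0 1 / ESTIMATE=EXP". The third is "CONTRAST '200 MG vs. 400 MG' TRTPN -1 1 / ESTIMATE=EXP". SAP 16.3.3.5 uses this model for MADRS response, and 16.3.3.6 does the same for remission.

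**Trend test.** The Appendix 3 code is "TABLE TRTP*RESP/CMH TREND", with no row order and no dose scores. Sections 16.3.3.3 (SDS composites) and 16.3.3.5 call for the test and give neither. Elsewhere in Appendix 3 the same variable takes values such as those in "IF MISSVAL=1 AND TRTP='200 MG' THEN TOTCFB" (tipping point) and "MODELOBS = (TRTP = 'Placebo" (placebo-based imputation). Appendix 1 introduces a different set of labels (Placebo, SEP-4199 200 mg, SEP-4199 400 mg) with "For outputs, treatment groups will be represented as follows and in that order"; that rule governs display.

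**The concern.** The first two lines give wrong output if they are followed as written. The geometric CV would be non-zero even for data with no spread, so the variability of drug concentrations and prolactin would be misreported. The dose-to-dose odds ratio and its interval would be the reciprocals of what the label says, so a reader would think the other dose had done better.

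The third line is incomplete rather than wrong. If placebo is scored above 400 mg, the test no longer addresses a dose trend in response, remission or the SDS composites. Treatment-emergent mania may also be reached, because SAP 17.6.1 analyses it in the same way as MADRS response.

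**Working it through.** The documents report no geometric CV, odds ratio or trend result, so there is no figure to reproduce. The check takes each line as written and compares it with what it should give.

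**(a) Geometric CV.** If log X is normal with variance v, the mean of X is exp(μ + v/2) and its variance is exp(2μ + v) × (exp(v) − 1). Hence CV² = exp(v) − 1, and the geometric CV is 100 × sqrt(exp(v) − 1). The SAP line is 100 × sqrt(exp(v − 1)). At v = 0 the first gives 0 and the second gives 100 × exp(−0.5) = 60.7%. Setting v = ln(1 + CV²):

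| True geometric CV | v | SAP formula prints |
|---|---|---|
| 10% | 0.010 | 61.0% |
| 30% | 0.086 | 63.3% |
| 50% | 0.223 | 67.8% |
| 100% | 0.693 | 85.8% |
| 150% | 1.179 | 109.3% |

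The two agree where exp(v) − 1 = exp(v − 1), that is at v = −ln(1 − exp(−1)) = 0.459, a CV of 76.3%. The SAP line is too high below that point and too low above it.

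**(b) Contrast.** Let b1 and b2 be the two treatment coefficients. With placebo as reference, coefficients `1 0` and `0 1` make b1 the log odds ratio of 200 mg against placebo and b2 that of 400 mg against placebo. Coefficients `-1 1` give b2 − b1, which exponentiates to the odds ratio of 400 mg against 200 mg.

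- Assumed response 50% (200 mg) and 60% (400 mg): the labelled ratio is (0.5/0.5)/(0.6/0.4) = 0.67; the code prints 1/0.67 = 1.50.
- With the rates exchanged, 1.50 prints as 0.67.
- Fitted example, assumed responders 33, 42 and 51 of 93 on placebo, 200 mg and 400 mg: coefficients `1 -1` give 0.678 (95% CI 0.381 to 1.208); the SAP's `-1 1` gives 1.474 (0.828 to 2.627). Both have p = 0.188.

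**(c) Trend test.** A default alphabetical sort of the Appendix 3 values gives 200 MG, 400 MG, Placebo. The same sort of the Appendix 1 labels gives placebo, 200 mg, 400 mg. With n = 93 per arm (SAP 3.4), overall response rate p and scores s with mean s̄:

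z = Σ n·p_i·(s_i − s̄) / sqrt(p(1 − p) · Σ n·(s_i − s̄)²)

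For assumed response 40/50/60% (placebo/200/400), the denominator is sqrt(0.25 × 93 × 2) = 6.82. In dose order the numerator is 93 × (0.60 − 0.40) = 18.6, so z = 2.73. With placebo scored highest it is 93 × (0.40 − 0.50) = −9.3, so z = −1.36.

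| Assumed response, placebo/200/400 | Dose order: z, p | Placebo last: z, p |
|---|---|---|
| 40/50/60% | 2.73, 0.006 | −1.36, 0.17 |
| 40/40/60% | 2.73, 0.006 | 0.00, 1.00 |
| 40/55/55% | 2.05, 0.041 | −2.05, 0.041 |
| 40/60/50% | 1.36, 0.17 | −2.73, 0.006 |

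A wrong order can therefore hide a trend, reverse its sign or produce a small p-value.

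**The case against.** **On (a)**, the finding rests on one bracket in text read from a PDF. Formula grouping in that text may be unreliable: both QTc formulas in SAP 17.3.1 read with the division by 1000 outside the root. The statistic is also descriptive and produced only where appropriate. The need to check the original page stands. But the brackets in the geometric CV line balance as printed and show no sign of a lost symbol.

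**On (b)**, the SAP text never plans a responder comparison of 200 mg with 400 mg. Sections 16.3.3.3 and 16.3.3.5 describe comparisons with placebo, and Section 8 leaves table content to templates that are not in the documents. Whether this odds ratio would be reported is therefore unknown. That limits the consequence, but the label and the coefficients still disagree.

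**On (c)**, Appendix 1 is the only place that formally defines treatment labels and their order, and its labels sort correctly. Appendix 3 is template code with placeholder names, and its tipping-point step describes a supposed dataset. This is fair: (c) is a gap, not a demonstrated error. The gap is still real. The values Appendix 3 shows for the 200 mg and 400 mg arms sort ahead of placebo, and its `LSMESTIMATE` statements also place placebo third, so a switch to that numeric treatment code would not settle the order.

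**Conclusion.** The concern holds, as a minor point. Parts (a) and (b) are wrong as written. The geometric CV has a floor of 60.7% and is right only at a true value of 76.3%, subject to confirming the bracket in the PDF. The contrast inverts the odds ratio and its interval but leaves the p-value and both placebo contrasts correct.

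Part (c) is conditional on how the treatment variable is stored, which the SAP does not say. Its p-values assume default alphabetical sorting with row-number scores. All response rates in (b) and (c) are assumptions, because the documents give none.

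The effect is confined to descriptive pharmacokinetic and prolactin summaries, to other efficacy endpoints, and possibly to the mania incidence analysis. The primary MMRM, CGI-BP-S, gatekeeping, alpha and sample size are unaffected.

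**What to change.** 1. In SAP 18.1, check the line against the original PDF and write: Geometric CV = Square Root(Exponential(Variance(log data)) − 1) × 100.
2. In Appendix 3, Logistic Regression, change the third contrast to `TRTPN 1 -1`, or keep the coefficients and relabel it as 400 mg against 200 mg.
3. In Appendix 3, Cochran-Armitage Test, use a numeric dose variable (0, 200, 400) as the row variable, so that order and scores do not depend on stored labels or on the numeric treatment code.

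These are three one-line corrections before unblinding. They need no new data and do not touch the primary analysis or alpha. If the SAP can no longer be amended, Section 20 already provides for describing and justifying such changes in the final report.
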